3. Each pile will then be sealed in an envelope and sent to the appropriate intervention site.
4. Each site will receive four sealed envelopes (of randomized cards) – one for each race/ethnic group.

5. Once received at each site, study staff/data collectors should not open the envelopes until the first participant's visit.
6. At each participant's baseline study visit, data collectors will select the appropriate race/ethnic group envelope and will choose the card at the top of the pile.
7. The treatment group printed on the card will determine the participant's treatment group.
8. The participant's study ID should be written on the card once the treatment group is determined and kept within the participant's study folder.
9. It is important to keep track of each participant's assigned treatment group so that each participant receives the appropriate juice and instructions.
10. Note: Randomization for each participant will occur in the same way. The randomly assigned cards within each envelope should not be shuffled at any time after opening the envelope, and data collectors should always choose from the same place (e.g., top of the pile).

Data Collection and Study Visits

Over the course of the six-week trial, participants will complete three study visits at baseline, week 3, and week 6. During the baseline visit, participants will complete the informed consent process before beginning any study-related activities.

All data collection measures and methods outlined in Aim 1 will be repeated at all three Aim 2 study visits. These measures include height (baseline-only), weight and body fat percentage, 10-hour fasting blood draw, RS-assessed skin carotenoid measurements (via the Veggie Meter® device), skin melanin measurements (via the Konica Minolta CM-700d Spectrophotometer), and a food frequency questionnaire (the National Cancer Institute's web-based Diet History Questionnaire III (DHQ-III)). Demographic questions (such as birthdate, age, sex, and race) will be asked at baseline only. Demographic questions with the potential for responses that could change over the course of the study (such as education, marital status, and income) will be asked at all three time points (baseline, week 3, and week 6). Sun exposure and tobacco use questions will be asked at each visit as well to track any changes to these behaviors.

Blood collected at the study visit will be sent to three sites for analysis and storage:

1. Eurofins Craft Technologies in North Carolina for carotenoid, glucose, and cholesterol analysis.
2. Baylor College of Medicine for genetic analyses to determine participant genetic ancestry and how variations in DNA can impact skin and blood carotenoid concentrations. Genetic results will not be provided to participants as they are research grade only. Whole genome sequencing will not occur.
3. East Carolina University for storage/banking of specimens for future research.

Juice Intervention

Juice was selected as a proxy for F&V consumption because it is practical to administer to a large group, can be purchased in a single lot for characterization, and is well tolerated by participants ([name], personal communication). The juice will be purchased from Campbell's in large lots (rather than small batches) to minimize potential variability in carotenoid content across all juices.

Providing a controlled juice product in lieu of a controlled diet affords greater control and ability to assess compliance (by providing a juice log to participants). Based on a detailed analysis of various potential fruit and vegetable juices conducted by [name], it was determined that the V8 Orange Carrot juice provides sufficient carotenoid mass to change skin carotenoid scores over a 6-week study duration. Thus, it was decided that participants in the two carotenoid-dose treatment groups will consume V8 Orange Carrot juice. Each 6 fl. oz of V8 Orange Carrot juice contains 6.1 mg total carotenoids (2.11 mg α-carotene, 3.97 mg β-carotene, 0.01

mg β-cryptoxanthin, 0.00 mg lycopene, and 0.01 mg lutein). Participants in the control group will consume Mott's Apple Juice (no carotenoids detected per [name] analysis).

Participants randomized to the moderate-dose treatment group will be asked to consume 6 fl. oz of V8 Orange Carrot juice each day. Participants randomized to the high-dose group will be asked to consume 12 fl. oz of V8 Orange Carrot juice (providing 12 mg total carotenoids/12 fl. oz) each day. A review article of studies to increase F&V intake found that in healthy adult populations, increases in fruit and vegetable intake ranged from about +0.1 to +1.4 serving/day,⁷¹ demonstrating the wide range of effects of such interventions and indicating that the Orange Carrot juice provides a dose of vegetables that would fall within this range.

After completing baseline measures and randomization, participants will receive the first three weeks' worth of Mott's Apple Juice (control) or V8 Orange Carrot Juice (moderate- or high-dose carotenoid-containing juice). Participants in the control group will receive Mott's Apple Juice in 64 fl. oz bottles while those in the moderate- or high-dose groups will receive V8 Orange Carrot Juice in 46 fl. oz bottles. Participants will also receive a pack of disposable, graduated 16 fl. oz cups to measure out the allotted daily amount. All participants will be instructed to drink their allotted amount of juice every day for 6 weeks with fat- or oil-containing meals (as carotenoids are absorbed more efficiently with lipids). The control group will be instructed to drink 6 fl. oz of apple juice/day (containing no carotenoids); the moderate-dose carotenoids group will be instructed to drink 6 fl. oz of orange carrot juice/day (containing 6 mg carotenoids/6 fl. oz); and the high-dose carotenoid group will be instructed to drink 12 fl. oz of orange carrot juice/day (containing 12 mg carotenoids/12 fl. oz). Participants will receive the same amount of juice again at the week 3 visit. In the event that a participant's body weight has increased by greater than 5% at the 3 week visit (from baseline), dietary education materials will be provided.

Juice Intervention and Study Measurements Timeline

Intervention Group	Baseline	Week 3 and Week 6
Control Mott's Apple Juice (6 fl. oz per day)	
• Obtain Consent• Collect variable measures: height, weight, skin carotenoids, skin melanin, and DHQ-III; demographics, sun exposure, and tobacco use	
• Collect variable measures: weight, skin carotenoids, skin melanin, and DHQ-III (to be completed the day before visit); demographics, sun exposure, and tobacco use• 10 hour fasting blood draw
Moderate-Dose V8 Orange Carrot Juice (6 fl. oz per day)	
• 10 hour fasting blood draw• Schedule week 3 and week 6 visits	
• Collect completed juice log/calendar (for weeks 1 – 3)
High-Dose V8 Orange Carrot Juice (12 fl. oz per day)	
• Provide participant with juice, instructions, pack of graduated cups, juice log/calendar (for weeks 1 – 3)• Study incentive (\$50)	
• Provide participant with juice and juice log/calendar (for weeks 4 – 6), additional cups if needed• Study incentive (\$100 at week 3 and \$150 at week 6)

Participant Incentive

All participants will receive \$300 across the 6-week study: \$50 at the baseline visit, \$100 at the week 3 visit, and \$150 upon completion of the final measures at week 6 visit. Participants at ECU and BCM will receive incentives through university issued Greenphire ClinCards. Participants at UMN will receive incentives as Target gift cards.

Intervention Adherence

One of the main challenges of the Aim 2 juice trial intervention is ensuring intervention adherence. To reduce risk of non-adherence, participants will be provided with an instruction sheet (see MOP Appendices) as well as a hard copy juice log (see MOP Appendices) on which we will ask them to mark the amount(s) of juice consumed each day. If all juice is not consumed, we will inquire why during the following study visit. Possible reasons include not liking the taste, spills, allergic reaction, someone else drinking the juice, and other. We will use this to measure dose and adjust for dose in our statistical analyses. Participants will also be reminded to maintain current diet and exercise habits. We will send all participants emails and allow them to opt in to receive text messages and/or phone calls (ensuring participant confidentiality) as periodic weekly reminders to drink the juice. The V8 Orange Carrot juice provides 60 kcal/6 fl. oz (or 120 kcal/12 fl. oz), and the control Mott's Apple Juice provides 90 kcal/6 fl. oz. We will provide an educational handout on the additional energy provided by the juices and dietary strategies to adjust caloric intake to remain isoenergetic.

Statistical Considerations

Power Calculation

Power calculations for Aim 2 are based off of Meinke et al.⁷⁰ which studied 30 adults (15 in the intervention group and 15 in the placebo control group) and used a dose of carotenoids (1.5 mg) most similar to the dose we are proposing. Based upon the data presented in Meinke et al. Figure 4, the standard deviation is 0.23 for 6-week relative skin carotenoid change. A sample size of 41 per group will have 90% power to detect 6-week relative skin carotenoids change of 1.13 vs. 1.28 when a one-sided two-sample t-test was used with a significance level of 0.05. With 20% attrition, we will need to enroll 52 per group, in each of three groups, for a total sample of 156.

Statistical Analysis

We hypothesize there will be RS-assessed skin carotenoid increases after 6 weeks of daily consumption of carotenoid-containing juice. To examine this hypothesis, we will compute changes in RS-assessed skin carotenoids from baseline to 3 weeks, from baseline to 6 weeks, and from 3 weeks to 6 weeks. Each level of change in RS-assessed skin carotenoids (as a response) will be analyzed using a general linear model to test the effects of carotenoid dose, melanin levels, and genetically determined ancestry, and dose x melanin and dose x genetically determined ancestry interactions. We will test baseline skin carotenoid level, baseline total plasma carotenoid level, baseline carotenoid intake and non-intervention carotenoid intake during the study, sex, age, skin hemoglobin index, blood total cholesterol, BMI status, body fat, season, and changes in self-reported total F&V intake in the model as potential covariates. If baseline confounding arises when the covariates differ significantly among the three intervention groups, a propensity score method will be adopted to balance the groups and control for the confounding. Similar analyses will be conducted when changes in plasma carotenoid are the response.

Plasma carotenoid analysis will be measured as described for Aim 1. We will also measure vitamin A status in the plasma as this can influence carotenoid absorption.

Interpretation

Upon successful completion of Aim 2, we will be able to translate RS intensity increases to an increase in F&V-derived carotenoid consumption. This will establish sensitivity of the RS device and enable better interpretation of findings from nutrition evaluation and surveillance studies using the RS device as an outcome measure.

Protection of Human Subjects

Aim 2 includes data from human subjects achieved by recruiting, enrolling, and collecting data from participants from North Carolina (East Carolina University, Greenville, NC), Minnesota (University of Minnesota, Minneapolis, MN), and Texas (Baylor College of Medicine, Houston, TX). Carotenoid analyses will occur at Eurofins Craft Technologies in Wilson, NC, and genetic analyses will occur at the USDA-ARS Children's Nutrition Research Center (CNRC) at Baylor College of Medicine in Houston, Texas. For Aim 2, we will conduct a 6-week randomized trial of a carotenoid-containing juice intervention among 156 racially and ethnically diverse participants in NC, MN, and TX. All study data will be stored in password-protected spreadsheets on password-protected computers and/or in locked filing cabinets.

Potential Risks

The primary risk for participants is risk of confidentiality breach. We will take all possible precautions to minimize this risk. Although there will be a link between a participant's data and their study-specific identification number, this link will be kept secure in password-protected computers available only to researchers directly involved in the study.

In addition, there is a risk of weight gain for Aim 2 participants who will be provided with Orange Carrot or apple juice. The Orange Carrot juice provides 60 kcal/6 fl. oz, and the apple juice provides 90 kcal/6 fl. oz. We will provide an educational handout on the additional energy provided by the juices and dietary strategies to adjust caloric intake as to remain isocaloric. If we see a >5% increase in body weight at the week 3 timepoint, staff will provide additional dietary education to the participant(s).

Upon study completion, we will share de-identified data with the scientific community, including investigators with appropriate credentials who wish to study relationships not proposed by investigators affiliated with the current project. The final dataset will not contain identifiers. However, to safeguard participants from potential breach of confidentiality/privacy, we will create a data-sharing agreement that ensures that 1) those with whom the data are shared will use it only for research purposes and will not identify any individual participant; 2) the data will be secured on password protected and appropriate computer technology; and 3) data will be destroyed or returned upon completion of data analysis.

Adequacy of Protection Against Risks

Study investigators and IRB-approved project staff will have access to individually identifiable data. If data are sent to investigators at other research sites, we will use ECU Institutional Review Board protocols to maintain confidentiality and protect identifiable information. All data will be stored in password-protected spreadsheets on password-protected computers and/or in locked filing cabinets. Study records will be kept a minimum of three years upon study completion.

Samples and data to be shared with researchers at the Baylor College of Medicine (for genetic analyses) and Eurofins Craft Technologies (for carotenoid analysis) will be stripped of any potential personal identifiers. DNA samples will be maintained in secured and alarm-protected labs at Baylor College of Medicine. Information on SNPs genotyped on the microarray have minimal established clinical utility at this time and individual-level

genotype results will not be returned. The SNPs on the array are commonly observed throughout world-wide populations, therefore, no unique genetic information will be generated, and there is consequently little to no risk for stigmatization, isolation or discrimination. The samples will be from independent/unrelated individuals; there is thus no risk for identifying non-paternity or undisclosed family relationships. The statistical analyses will not be able to reveal potential incest. Although analyses will evaluate general genetic ancestry, existing constitutional statutes ensure that there is thus no associated risk for discrimination. Analyses will focus on aggregate data that will be shared with the public and researchers through the usual dissemination mechanisms, including publications and presentations at scientific meetings.

To ensure high quality data management, the Research Electronic Data Capture (REDCap) system will be used. REDCap is a secure, HIPAA-compliant, web-based application for building and managing research databases. REDCap provides automated export procedures for data downloads to Excel and common statistical packages including SPSS, SAS, Stata, and R, a built-in project calendar, a scheduling module, and reporting tools (<http://www.ecu.edu/itcs/help/redcap>). [name] has been trained in the use of REDCap and our team will utilize the following features to maximize data quality and management:

- The online survey building and administration tool, used by research teams in NC and MN

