Meinke et al.⁷⁰ studied 30 adults (15 in the intervention group and 15 in the placebo control group) and used a dose of carotenoids (1.5 mg) most similar to the dose we are proposing. Based upon the data presented in Meinke et al. Figure 4, the standard deviation is 0.23 for 6-week relative skin carotenoid change. Additionally, a shortened duration (6 week vs. 8 weeks) increases the likelihood of higher intervention adherence. Intervention duration and power calculations for Aim 2 are based off of Meinke et al.

[name]'s recent analyses of the variables predictive of the change in plasma lycopene and β -carotene in response to a 3 week intervention of 0, 1, or 2 cans of tomato juice (delivering 21 mg lycopene, 1 mg β -carotene/can) showed that while dietary intervention group was the major explanatory variable, baseline plasma lycopene, body mass, and nutrigenetic interactions explained an additional 22% of variance in plasma lycopene response (Figure 3). Genetics, non-intervention β -carotene intake, and diet explained 62% of the variance in plasma lycopene responses to the intervention.⁶⁸ These studies were conducted in a primarily non-Hispanic White population highlighting the need for additional research in racially and ethnically diverse populations.

We have found SNPs in the carotenoid metabolizing enzyme, β -carotene oxygenase 1 (BCO1), are associated with plasma and tissue carotenoid responses over a 3-week feeding period. As shown in Figure 3, 5% of the variance in plasma lycopene and 20% of the variance in β -carotene responses were explained by BCO1 SNP genotypes. The BCO1 rs12934922 SNP highlighted here has also emerged in another publication⁶⁹ to effect plasma β -carotene responses to a dietary intervention because it impacts the efficiency with which BCO1 enzymatically cleaves β -carotene. While these preliminary data are intriguing, the current study is designed to take a higher dimensional approach to the study of the genetic

[figure not shown]

Figure 4: Mean and SEM of skin carotenoids relative to initial values of the placebo and verum groups measured by the two SRSS and the RRS systems.

Study Design & Methods

Rationale/Strategy

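### The 90% power belongs to a single one-sided 6-week t-test, while the analysis section plans a three-arm dose model on three unranked intervals with no primary dose test or multiplicity rule

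*Combined protocol and SAP*

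**What the plan says.** **Sizing.** The Power Calculation takes an SD of 0.23 for 6-week relative change from an earlier two-group study and reports "90% power to detect 6-week relative skin carotenoids change of 1.13 vs. 1.28 when a one-sided two-sample t-test was used" at a 0.05 level with 41 per group. It then allows 20% attrition and multiplies by three arms.

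**Hypothesis.** The Statistical Analysis section opens: "We hypothesize there will be RS-assessed skin carotenoid increases after 6 weeks of daily consumption of carotenoid-containing juice". The Objective says much the same.

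**Analysis.** To examine that hypothesis the section computes "changes in RS-assessed skin carotenoids from baseline to 3 weeks, from baseline to 6 weeks, and from 3 weeks to 6 weeks". It continues: "Each level of change in RS-assessed skin carotenoids (as a response) will be analyzed using a general linear model". The stated purpose of that model is "to test the effects of carotenoid dose, melanin levels, and genetically determined ancestry"; dose-by-melanin and dose-by-ancestry interactions are tested as well. It adds: "Similar analyses will be conducted when changes in plasma carotenoid are the response".

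**Left open.** No section ranks the three intervals, names a primary dose contrast, gives the sidedness of the model tests, or sets a testing order or multiplicity rule.
- *Form of dose.* The Juice Intervention section gives three arms at 0, 6 and 12 mg. On juice-log intake, Intervention Adherence says "We will use this to measure dose and adjust for dose in our statistical analyses". Dose could therefore be a three-level factor or a quantitative term, and assigned or consumed.
- *Scale.* The power input is relative change; the analysis text says only that changes will be computed.
- *Arms.* The source figure is captioned "Mean and SEM of skin carotenoids relative to initial values of the placebo and verum groups", which is two groups. This trial has three, and no section says which of them 1.13 and 1.28 describe.

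**The concern.** A power figure is a property of one test. Here the test that carries the 90% does not appear in the analysis section, and the analysis that does appear has no stated power. A dose effect with 2 df has no one-sided version, so the sidedness used for sizing cannot carry over unless a 1-df contrast is named.

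The second issue is error control. All three intervals are introduced as ways of examining a single hypothesis, and none is given precedence. Read literally, a positive dose test at 3 weeks, or from week 3 to week 6, could be offered as support for the 6-week statement. The aim is to establish the sensitivity of the device, and that conclusion needs one dose test whose false-positive rate and power are known beforehand.

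**Working it through.** **Inputs.** From the Power Calculation: means 1.13 and 1.28 (difference 0.15), SD 0.23, one-sided 0.05, 90% power, 20% attrition, three groups. From Study Population: 160 to be enrolled. From Measurement and Reporting of Adverse Events: 85% retention goal. Assumed: equal arms, common SD, no covariate gain, and, where stated, a mean for the third arm.

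**1. Reproduce the plan.** Normal approximation: n = 2(1.645 + 1.282)² × (0.23/0.15)² = 2 × 8.56 × 2.351 ≈ 40.3. The exact noncentral-t solution is 40.96. Both round up to 41. Then 41/0.8 = 51.25, rounded up to 52, and 52 × 3 = 156. The plan's figures reproduce.

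**2. Single contrast, 41 per arm.** Noncentrality = 0.15 / (0.23 × √(2/41)) = 2.953, df = 80.
- One-sided 0.05 (critical value 1.664): 90.0%.
- Two-sided 0.05 (critical value 1.990): 83.1%.

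**3. Linear dose trend over 0/6/12 mg.** With equal spacing and equal arms the slope contrasts the two end arms, so noncentrality is again 2.953, now with df = 121. Taking 1.13 and 1.28 as the end arms and 1.205 between them, power is 90.2% one-sided and 83.4% two-sided.

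**4. Dose as a three-level factor (2-df F test, error df 120, critical value 3.07).** λ = 41 × Σ(mean − grand mean)² / 0.23².

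| Assumed arm means | Sum of squares | λ | Power |
|---|---|---|---|
| 1.13 / 1.205 / 1.28 | 0.01125 | 8.72 | 74.5% |
| 1.13 / 1.13 / 1.28, or 1.13 / 1.28 / 1.28 | 0.0150 | 11.63 | 86.4% |
| 1.13 / 1.28 / 1.355 | 0.02625 | 20.34 | 98.5% |

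**5. With 160 enrolled (single contrast).**
- 80% retention: 160 × 0.80/3 = 42.7 per arm, giving 84.6% two-sided and 91.0% one-sided.
- 85% retention: 160 × 0.85/3 = 45.3 per arm, giving 86.7% two-sided and 92.5% one-sided.

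**6. False positives under no effect.** Three independent tests at 0.05 would give 1 − 0.95³ = 14.3%. These are not independent, because the 3-to-6-week change is the 6-week change minus the 3-week change. Simulating the 2-df test on all three change scores with 41 per arm gives about 12.5% with equally variable, independent visit errors, and 11.9% if visit errors correlate 0.8 between adjacent visits. At week 6 alone, two unadjusted one-sided active-versus-control contrasts sharing a control give about 8.8%.

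**7. What would return the two-sided contrast to 90%.**
- A true difference of about 0.167: noncentrality 0.1667 / (0.23 × √(2/41)) = 3.28.
- Covariates with R² of about 0.184: residual SD 0.23 × √(1 − 0.184) = 0.208, noncentrality 3.27, df 119.

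The documents give no R².

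**The case against.** **Week 6 and direction are not in doubt.** The Objective, the Preliminary Studies rationale for a 6-week duration, the sizing and the hypothesis all point to week 6, and the hypothesis is directional. The other two intervals can be read as describing the time course. This stands: a reader might infer that the plan has no endpoint time or direction, and the text does not support that. What remains is that week 6 is not labelled primary and that all three intervals are introduced as examining the one hypothesis.

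**The sample size may be adequate as it is.** This also stands. A reader might infer that the trial is underpowered or that N is wrong. The documents do not support that, because a one-sided 1-df trend or contrast keeps 90%, and the juice-log sentence is compatible with a quantitative dose. The lower figures apply only if the test is two-sided or has 2 df, the difference is exactly 0.15, and covariates bring nothing. The planned model includes candidate covariates such as baseline skin carotenoids, so some gain is possible. The figures above also omit the planned interactions. In addition, the Power Calculation puts the source dose at 1.5 mg, against 6 and 12 mg here, so the true difference need not be 0.15. How the response scales with dose is not given.

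**1.13 and 1.28 are naturally control and active.** Given the caption, that is plausible. It still leaves open which active arm is meant.

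None of this supplies a named primary dose test, the sidedness of the model tests or a multiplicity rule.

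**Conclusion.** The point holds as a mismatch between the powered test and the planned analysis; it does not show an error in the sample size. The 90% is true of one one-sided two-sample test of 6-week relative change that the analysis section does not plan.

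The sizes are conditional. The false-positive chance of about 12% to 12.5% requires a 2-df dose test at 0.05 on every interval, any positive being accepted as support, and the assumed visit-error structure. It should not be read as a rate the plan is certain to incur. If two-sided testing is used, the chance of missing a difference of 0.15 is about 17% at 41 evaluable per arm, or 13% to 15% with 160 enrolled, rather than 10%, before any covariate gain. For a 2-df test the 75% to 86% range assumes the third arm lies at or between 1.13 and 1.28; power is higher if an arm exceeds 1.28. The gap in pre-specification does not depend on these assumptions. It should be fixed, and wording is enough.

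**What to change.** Keep N and amend the Statistical Considerations text.

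1. Label baseline-to-6-week relative change in skin carotenoids the primary response. Label the 0-to-3-week and 3-to-6-week changes and all plasma analyses secondary.
2. Name one 1-df primary dose test on randomised arm at 6 weeks: either a linear trend over 0/6/12 mg or high dose versus control. If the trend is chosen, report both active-versus-control differences with confidence intervals as secondary. If high versus control is chosen, test moderate versus control only if it succeeds.
3. State the sidedness in the analysis section and match the power statement to it. Keep 90% only for a single one-sided primary test. Otherwise state about 83% power, two-sided 0.05, for a difference of 0.15 with 41 evaluable per arm (90% for about 0.167), before any covariate gain. These figures apply to the ratio or percent-change scale; recompute them if a log ratio is used.
4. State which arms 1.13 and 1.28 describe.

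**Cost.** No extra participants. If two-sided testing is chosen, the stated power falls from 90% to about 83% (85% to 87% with 160 enrolled). The other intervals lose confirmatory status. The follow-on moderate-versus-control test may be weak: if that arm sits midway (assumed difference 0.075), its power is about 43% one-sided or 31% two-sided, so it should be reported with a confidence interval.

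### Three separate change-score models serve one 6-week hypothesis with no primary window, so week-3 data cannot inform the week-6 result

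*Combined protocol and SAP*

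**What the plan says.** Under Statistical Analysis the hypothesis is "We hypothesize there will be RS-assessed skin carotenoid increases after 6 weeks of daily consumption of carotenoid-containing juice". To examine it, changes are computed "from baseline to 3 weeks, from baseline to 6 weeks, and from 3 weeks to 6 weeks", and "Each level of change in RS-assessed skin carotenoids (as a response) will be analyzed using a general linear model". Each model tests dose, melanin, genetic ancestry and two interactions with dose, with a list of candidate covariates. Plasma carotenoid changes are to be analysed in the same way.

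The Power Calculation section uses only the 6-week change. Its provision for loss is "With 20% attrition, we will need to enroll 52 per group, in each of three groups, for a total sample of 156". Under Participant Ineligibility Post-Screening, anyone who falls ill before the week 3 or week 6 visit is withdrawn and may start again about two months later.

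The document names no repeated-measures model, analysis population, missing-data method, primary window or multiplicity rule.

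**The concern.** A general linear model of a change score uses only people with both visits of that window, unless some other handling is specified, and none is. Someone measured at baseline and week 3 but absent at week 6 enters the 0-3 week model only. Enrolling extra people restores numbers, but it does not correct for who leaves.

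Week 3 should carry much of the week-6 information. The Preliminary Studies section gives a 7.9-day half-life for β-carotene, the main carotenoid in the study juice. That implies 1 - 2^(-21/7.9) = 84% of plateau at week 3 and 1 - 2^(-42/7.9) = 97% at week 6.

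Loss that differs by arm is possible: the arms differ in product and volume, and the Intervention Adherence section treats adherence as a main challenge. Separately, three windows under one hypothesis leave open which result decides it.

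**Working it through.** **The plan's own figure.** Inputs from the Power Calculation section: an SD of 0.23, a one-sided t-test at alpha 0.05, and this target: "A sample size of 41 per group will have 90% power to detect 6-week relative skin carotenoids change of 1.13 vs. 1.28". The difference is thus 0.15.

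- n per group = 2 × (1.645 + 1.282)² × 0.23² / 0.15² = 40.3, rounded up to 41. Power at 41 is 90.5% (normal) or 90.0% (noncentral t).
- 41 / 0.8 = 51.25, rounded up to 52; 3 × 52 = 156.

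The sample size reproduces and is not in dispute. Everything below is on that relative-change scale. Two inputs are not in the documents and are assumed over a range: ρ, the correlation between the 0-3 and 0-6 week changes, and the number per arm still present at week 3.

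**Precision.** With 41 completers per arm and n3 seen at week 3, the likelihood-based variance of an arm's week-6 mean change is 0.23² × [(1 - ρ²)/41 + ρ²/n3]. Power is Φ(0.15/SE - 1.645).

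| n3 per arm | ρ = 0.5 | ρ = 0.7 | ρ = 0.9 |
|---|---|---|---|
| 41 (all loss before week 3) | 90.5% | 90.5% | 90.5% |
| 46 | 91.1% | 91.8% | 92.6% |
| 52 (all loss after week 3) | 91.8% | 93.0% | 94.5% |

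The gain is 0 to 4 points.

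**Bias.** Let z be the standardised week-3 change within an arm, and let the log-odds of leaving after week 3 be a - b·z, with a set to give the assumed loss. Let δ be the mean of z among those who stay. The completers' between-dose difference is then biased by ρ × 0.23 × (δ_juice - δ_control).

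- Same selection in each arm relative to its own mean: the δ terms cancel and the bias is 0.
- Same absolute week-3 rule in both arms (b = 1.2, week-3 effect assumed 0.10, ρ 0.5 to 0.9): -0.007 to -0.013.
- Poor early responders leave the juice arm only, 20% loss, half to three quarters of those lost having been seen at week 3. Loss after week 3 is then 0.10/0.90 = 11% to 0.15/0.95 = 16% of those present. With b = 1, δ = 0.100 to 0.139. For ρ 0.6 to 0.8, the bias is 0.6 × 0.23 × 0.100 = +0.014 to 0.8 × 0.23 × 0.139 = +0.026.
- As above, but all 20% lost after week 3 and b = 1.2, so δ = 0.197. For ρ 0.5 to 0.9, the bias is 0.5 × 0.23 × 0.197 = +0.023 to 0.9 × 0.23 × 0.197 = +0.041, or 15% to 27% of 0.15.

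In simulations of 52 per arm, a likelihood analysis using week 3 brought the bias to about zero wherever dropout depended on the week-3 value. When juice-arm dropout depended instead on the unseen week-6 value, the bias was about +0.045 for completers and still +0.009 to +0.034 with the likelihood analysis.

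**Error rate.** The 0-6 week change is the sum of the other two, so the three tests are correlated. I simulated three z-tests with ρ from 0.5 to 0.9 and the week-3 SD at 0.7 to 1.0 times the week-6 SD. The chance of at least one false positive per contrast is 0.100 to 0.122 two-sided (0.095 to 0.126 one-sided), against 0.143 for three independent tests. If week 6 alone decides, it is 0.05.

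**The case against.** The case against rests on several points.

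- **Week-3 data are not thrown away.** A reader might infer that they are, but people lost after week 3 still enter the 0-3 week model. They are missing only from the 0-6 and 3-6 week models. This stands.
- **The mechanism is not documented.** The only route of loss described is illness before a visit, with no stated link to response. Both juices are tasted before enrolment, payment is weighted to week 6, reminders are sent, intake is logged and adjusted for, and the retention goal is 85%. This stands, so the bias figures are scenarios and not forecasts. People lost before week 3 have no follow-up data for any model to use.
- **Poor responders leaving is not enough to inflate the dose effect.** A reader might infer that it is. With equal relative selection the between-dose difference is unbiased, and a common absolute rule shrinks it. This stands for the difference between doses. It does not protect each arm's mean increase, which the Interpretation section wants to translate into intake.
- **The plan does not say that any window counts as success.** The hypothesis and the power calculation both point to week 6, so inflated type I error cannot be read off the text as it stands. But nothing makes week 6 primary either.
- **A figure that adds plasma is not supported.** The pilot's skin-plasma correlation of 0.71 is between levels in 30 people, not between changes, so it cannot supply a combined error rate.

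**Conclusion.** The point holds in a limited form. The plan uses three separate models for one 6-week hypothesis, names no primary window, and lets week-3 data play no part in the week-6 result for people lost in between. The precision cost is small, at 0 to 4 power points. The between-dose bias could be slightly negative, zero, or up to about +0.04 on 0.15, depending on whether selection differs by arm. A joint model removes it only if dropout depends on observed data. The error rate reaches about 10-12% per contrast only if any window is allowed to count.

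These sizes rest on assumed dropout timing, correlation and selection strength. The documents do not show that the 6-week effect will be overstated. They leave the question open where a cheap change would close it.

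**What to change.** 1. Name the week-6 dose contrast for RS skin carotenoids as the single primary test. State which dose levels it compares (or a dose trend), its sidedness and its alpha. This is what settles the multiplicity; the longitudinal model alone does not. A Bonferroni split over three windows would instead need 55 evaluable per arm, and 41 would give 79.5% power.
2. Fit one likelihood-based longitudinal model to baseline, week 3 and week 6, including all randomised participants with any data. Use visit × dose terms, a common baseline mean across arms and unstructured covariance. Keep the planned melanin, ancestry, dose × melanin and dose × ancestry terms, by visit.
3. Report the 0-3 and 3-6 week windows as secondary contrasts of that model, and the same model for plasma as secondary.
4. State the missing-at-random assumption and add a sensitivity analysis for dropout that depends on unseen values.
5. Count each person once in the analysis if they restart after illness, and say which course of data is used.

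The cost is SAP wording, standard mixed-model code and slightly more analysis work, with no change to enrolment or visits. The downside is reliance on missing at random, which step 4 addresses.
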